16.1. Informed consent process

Inclusion in the study will occur only if the subject gives written informed consent. It is the responsibility of the Investigator / designee to obtain written informed consent from each individual participating in this study, after adequate presentation of aims, methods, anticipated benefits, and potential hazards of the study. If needed, the person will be given time to discuss the information received with members of the community or family before deciding to consent. The subject will be asked to provide written and signed consent.

If new safety information results in significant changes in the risk/benefit assessment, the consent form should be reviewed and updated if necessary. All subjects

(including those already being treated) should be informed of the new information, given a copy of the revised form and give their consent to continue in the study.

16.2. Compensation of volunteers

The Sponsor agrees to abide by the Association of the British Pharmaceutical Industry Guidelines for medical experiments in healthy human volunteers (2012 edition)²⁴ and undertakes to compensate the subjects for injuries which are considered, on the balance of probabilities, to have arisen as a result of their participation in the trial.

16.3. Insurance and Liability

DNDI is insured to indemnify the Investigator against any claim for damages brought by a subject who suffers from a research related injury during the performance of the trial according to the protocol, except for claims that arise from malpractice and/or negligence.

In accordance with local regulations, DNDI will contract insurance for all study participants.

16.4. Reporting of Safety Issues and Serious Breaches of the Protocol or ICH GCP

In the event of any prohibition or restriction imposed by an applicable Competent Authority in any area of the World, or if the Investigator is aware of any new information which might influence the evaluation of the benefits and risks of the IMP, DNDI should be informed immediately.

In addition, the Investigator will inform DNDI immediately of any urgent safety measures taken by the Investigator to protect the study subjects against any immediate hazard, and of any serious breaches of this protocol or of ICH GCP that the Investigator becomes aware of.

DNDI is responsible for reporting any serious breaches of the protocol or of ICH GCP to the UK Regulatory Authorities.

28 MAR 2018

Date

[name]
Head of Translation, DNDi

[figure not shown]

Signature

27 March 2018

Date

[name]
Filarial Team Leader, DNDi

Signature

27 March 2018

Date

3 Introduction

This Statistical Analysis Plan (SAP) is based on the current trial protocol (version 3, 1 February 2018). Where statistical methods differ substantially between this SAP and the protocol, that will be identified in this document.

This SAP describes the datasets and the statistical methods to be used for the reporting and analysis of all data collected during the trial.

The randomisation code will not be broken before this SAP is finalised. If a future protocol amendment necessitates a substantial change to the statistical analysis of the trial data, this SAP will be amended accordingly. If, after database lock, additional analyses are required to supplement the planned analyses described in this SAP, those unplanned analyses will not be described in an amended SAP, but they will be identified in the integrated clinical study report (CSR). Any deviations from this SAP will be documented in the CSR.

This SAP has been written in consideration of the following guidelines:

- International Conference on Harmonization (ICH) E9, Guidance for Industry: Statistical Principles for Clinical Trials (ICH E9 1998)¹; and
- ICH E3, Guidance for Industry: Structure and Content of Clinical Study Reports (ICH E3 1995)².

Pharmacokinetic analysis will be done using WinNonlin v7 on a Windows PC. Statistical analysis will be done using SAS[®] 9.3 on a Windows PC.

4 Study Objective(s) and Endpoint(s)

4.1 Study Objective(s)

4.1.1 Primary Objective

To investigate the pharmacokinetics, including relative bioavailability and food effect, of two new immediate release (IR)-tablet formulations of emodepside in comparison to the liquid service formulation (LSF) oral solution.

4.1.2 Secondary Objectives

To investigate and compare safety and tolerability of single oral doses of emodepside formulations in healthy subjects.

4.2 Study Endpoint(s)

4.2.1 Primary Endpoint

- Based on the plasma concentration–time data, the following PK parameters of emodepside will be calculated:
 - Main: AUC_{0-7d} , $AUC_{0-7d}/Dose$, C_{max} , $C_{max}/Dose$

4.2.2 Secondary Endpoints

- Safety and Tolerability Variables:
 - Adverse Events (AEs)
 - Physical and neurological examination findings
 - Vital signs (BP and HR),
 - 12-lead ECG (HR, PR, QRS, QTcB, QTcF), will be analysed ad hoc for safety and for the final data base and report by central reading
 - Clinical laboratory tests
 - Haematology: haemoglobin, haematocrit, mean corpuscular volume (MCV), mean corpuscular haemoglobin (MCH), mean corpuscular haemoglobin concentration (MCHC), platelets, reticulocytes, white blood cells (WBC) including differential, red blood cells (RBC);
 - Coagulation: activated partial thromboplastin time (aPTT), prothrombin time (PT);
 - Biochemistry: serum aspartate aminotransferase (AST), alanine aminotransferase (ALT), alkaline phosphatase (AP), gamma-glutamyl transpeptidase (GGT), lactate dehydrogenase (LDH), creatine kinase (CK), amylase, lipase, glucose, cholesterol (HDL, LDL, total), triglycerides, creatinine, urea, uric acid, bilirubin (total and conjugated), total protein, sodium, potassium, calcium, chloride and magnesium;
 - Urinalysis: by dipstick – glucose, ketone bodies, specific gravity, occult blood, pH, proteins, leucocytes, bilirubin, urobilinogen, nitrites, and microscopy (reflex).

4.2.3 Exploratory Endpoints

- Pharmacokinetic:
 - $AUC_{0-7d,norm}$, $C_{max,norm}$, $t_{1/2,0-24h}$, $t_{1/2,0-7d}$, t_{max} , MRT, points terminal

4.3 Statistical Hypotheses

Except for the analysis of pharmacokinetic data, no formal statistical testing will be done.

5 Study Design

This is a single-centre, open-label, randomized, parallel-group relative bioavailability study in healthy men. The study will be done in 2 parts, as follows:

- Part 1 – single oral doses of 5 mg emodepside will be tested:
 - Part 1a – the LSF (reference formulation) and 2 new IR-tablet formulations (test formulations) will be administered in the fasted state.
 - Part 1b – the 2 new IR-tablet formulations will be administered in the fed state (high-fat, high-calorie meal).
- Part 2 – single oral doses of 10 mg (2 x 5 mg) emodepside will be tested: depending on the results from Part 1, one or both IR-tablet formulations will be administered in the fasted state.

The treatments in each study part are summarised in Table 1.

Table 1. Planned treatments by dose, formulation and condition

Part	Treatment	Formulation, dose and condition	Number of subjects
Part 1a	A	5 mg emodepside LSF, fasted	12
	B	5 mg emodepside IR-tablet #406, fasted	12
	C	5 mg emodepside IR-tablet #416, fasted	12
Part 1b	D	5 mg emodepside IR-tablet #406, fed	12
	E	5 mg emodepside IR-tablet #416, fed	12
Part 2	F*	2 x 5 mg emodepside IR-tablet #406, fasted	12
	G*	2 x 5 mg emodepside IR-tablet #416, fasted	12

* one or both treatments may be tested, depending on results from Part 1

Up to 84 healthy volunteers will be enrolled, in up to 7 treatment arms made up of 12 subjects each.

The 36 subjects in Part 1a will be randomised to one of 3 treatments (A, B or C). The 24 subjects in Part 1b will be randomised to one of 2 treatments (D or E). Parts 1a and 1b may proceed in parallel, or may be done sequentially.

After at least 10 subjects in each arm have received treatment in Part 1, and data up to 72 h after dosing are available, there will be a Dose Decision Meeting to determine which treatment(s) will be tested in Part 2 (see section 7.5).

In Part 2, either treatment F, G or both F and G will be tested. There will be 12 subjects enrolled for each treatment tested. If both treatments are tested, they will be done in parallel, and subjects will be randomised to one of the 2 treatments.

The study will be performed in a single site specialized in Phase 1 studies.

6 Time and Events Table

Procedure	Screening		Inpatient														Follow-up							
	Day -28 to -2	Day -1 hours	Day 0												Day 1		Day 2		Day 3		Day 5		Day 7	
			-1	0	0.25	0.5	1	1.5	2	2.5	3	4	6	8	12	24	36	48	72	120	168			
Subject demographics and informed consent	X																							
Inclusion/exclusion criteria - Eligibility check	X	X																						
Medical history/prior medication	X																							
Inpatient stay			← →																					
Administration of emodepside ¹																								
Outpatient visit	X																				X	X		
Drugs of abuse screen	X	X																						
Alcohol breath test	X	X																						
Physical and neurological examination ²	X	X																		X	X	X	X	X
Vital signs ³	X		X			X	X	X	X		X	X					X	X	X	X	X	X	X	
12-lead safety ECG ⁴	X		X			X	X	X	X		X	X					X	X	X	X	X	X	X	
Laboratory safety tests ^{5,6}	X		X																X	X	X	X	X	
Serology ⁷	X																							
Blood samples for assay of emodepside ⁶				X		X	X	X	X	X	X	X	X	X	X	X	X	X	X	X	X	X		
AE questioning ⁸			← →																					

1. Subjects in Part 1a and Part 2 will fast for 10 h before until at least 4 h after dosing. Subjects in Part 1b will be given a high-calorie, high-fat breakfast approximately 30 min before dosing, which they must finish at least 5 min before dosing. Standard meals will be served at approximately 5 h (lunch), 8 h (snack) and 12 h (dinner) after dosing on Day 0. Procedures scheduled at the same time as a meal will be completed before the meal.
2. A full physical examination will be done at Screening and Follow-up. A brief (symptom-directed) physical examination and short neurological examination will be undertaken at all other time points. Any abnormalities will trigger a full neurological examination and/or opening of an AE as appropriate. Height, weight and body mass index (BMI) will be assessed at screening, and weight will be assessed on Day -1.
3. Vital signs will comprise supine blood pressure and heart rate. Subjects should rest in the supine position for at least 10 min before vital signs measurements. Vital signs will be measured in triplicate at screening and pre-dose (-1 h); single measurements at all other time points. Body temperature will be measured on day -1.

4. Subjects should rest in the supine position for 10 min before ECG measurements. Measurement in triplicate at screening and pre-dose (−1 h); single measurements all other time points.
5. Blood and urine samples for clinical laboratory safety tests (haematology, biochemistry, coagulation and urinalysis).
6. Subjects should rest in the supine position for 10 minutes before blood is drawn (if possible).
7. Serology tests will comprise HIV 1 & 2 and hepatitis B & C.
8. Adverse event monitoring will be done throughout the study, but scheduled questioning will be done at the time points of scheduled blood draws.

7 Planned Analyses

7.1 Interim Analyses

The decision to go ahead with one or both treatments in Part 2 (10mg [2 x 5mg] of IMP) will be made based on the safety, tolerability and PK of the treatments in Part 1 (5mg of IMP).

The dose decision will be made by the Safety Review Group (SRG) at the Safety Review Meeting. The treatments will not be decided until the SRG has reviewed the safety, tolerability and PK data of at least 10 subjects per treatment. Safety, tolerability and PK data up to a minimum of 72 h post-dose should be reviewed before a decision can be made.

7.2 Final Analysis

Each part of the study (Part 1 and Part 2) will have a separate database and will be analysed and reported separately. Each database will be locked once all subjects have completed, data have been entered, all queries resolved and protocol deviations identified for that part of the study. Final analyses will be carried out following database lock for each individual part of the study.

8.1 Sample Size Assumptions

No formal statistical sample size estimation has been performed, due to the exploratory nature of this study.

10 subjects per treatment arm is considered sufficient to examine the safety and tolerability of emodepside, as well as the PK after single doses. However, 12 subjects will be recruited and enrolled per treatment arm to ensure a minimum of 10 evaluable subjects complete the study.

9 Analysis Populations

The following populations will be identified:

Safety Population: All subjects who received at least one dose of IMP.

PK Concentration Population: All subjects who received at least one dose of IMP and for whom a PK sample has been analysed.

PK Parameter Population: All subjects in the PK Concentration Population for whom PK parameters can be derived.

In all populations, treatment will be assigned based upon the treatment subjects actually received, regardless of the treatment to which they were randomized.

The primary endpoint will be analysed using the PK Parameter population.

9.1 Analysis Datasets

All analysis datasets will be based on observed data, except as outlined in Section 12.2.

10 Treatment Comparisons

The treatment comparison of interest is test (IR-tablet formulations) versus reference (LSF).

11 General Considerations for Data Analyses

11.1 Data Display Treatment and Other Subgroup Descriptors

The sort order for treatment groups will be treatment in ascending dose order. When a total column is included, it immediately follows the treatment groups which it aggregates.

Listings of data will be sorted and displayed by treatment group, subject number, and also by date and time if applicable.

The treatment descriptions to be used on all tables and listings are:

Treatment Groups	Short Description
Emodepside LSF 5 mg [fasted]	LSF 5 mg [fasted]
Emodepside IR-tablet #406 5 mg [fasted]	IR #406 5 mg [fasted]
Emodepside IR-tablet #416 5 mg [fasted]	IR #416 5 mg [fasted]
Emodepside IR-tablet #406 5 mg [fed]	IR #406 5 mg [fed]
Emodepside IR-tablet #416 5 mg [fed]	IR #416 5 mg [fed]
Emodepside IR-tablet #406 10 mg [fasted]	IR #406 10 mg [fasted]
Emodepside IR-tablet #416 10 mg [fasted]	IR #416 10 mg [fasted]

11.2 Conventions for Summary Statistics and Data Displays

The minimum set of summary statistics for numeric variables will be: n, mean, standard deviation (or standard error), median, minimum, and maximum. 95% confidence intervals will be presented where appropriate for data interpretation.

Categorical data will be summarised in frequency tables with n and percentage. Summaries of a categorical variable will include all recorded values.

The minimum and maximum values will be presented with the same number of decimal places as the raw data collected on the CRF (or to 3 significant figures for derived parameters less than 100 and as integers for values more than 99). The mean and percentiles (e.g. median, Q1, and Q3) will be presented using one additional decimal place. The standard deviation and standard error will be presented using two additional decimal places.

12 Data Handling Conventions

12.1 Premature Withdrawal and Missing Data

All subjects who withdraw prematurely from the study and received the study drug will be included in the statistical analyses.

If a subject completes the treatment period but has missing data, then this will be made apparent in the subject listings. Missing data will not be imputed except for as outlined in Section 12.2.

If the study is prematurely discontinued, all available data will be listed and a review will be carried out to assess which statistical analyses are still considered appropriate.

Data collected at unscheduled time points during the study will not be used in the summaries or data analyses. They will be included in the listings.

If time information (i.e. hours and/or minutes) for adverse events or concomitant medication is missing, but the day is present, then the time will be calculated in days. If date information is partial or missing, then any derived times (e.g. AE start time from last study medication) will be listed as missing.

Conventions for handling missing plasma concentrations are given in Appendix B.

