8.8. Sampling time points and additional tests

With the Sponsor's approval, additional time points may be introduced, and changes to time points may be made, if there is reason to believe that the change might improve the quality of the data (for example, if it is believed that an important effect of emodepside is occurring at a time when no measurements are scheduled), or if extra procedures are needed in the interest of subject safety. However, the total volume of blood taken in the trial will not exceed the value given in Section 8.10 unless in the opinion of the Investigator, it's in the subject's best interest that extra blood is taken for additional safety tests.

An additional 48 h residence in the ward, and additional outpatient visits, will be permitted in the event of a technical failure, and/or if extra observations or samples of blood are needed for safety purposes.

In the case of any post-dose samples for PK analysis, the following will not be regarded as protocol deviations:

- Deviations of not more than 5 min on measurements scheduled up to and including 4 h after dosing;
- Deviations of not more than 15 min on measurements scheduled from after 4 h to 24 h after dosing;
- Deviations of not more than 1 h on measurements scheduled more than 24 h after dosing; and
- Deviations of not more than 3 h on measurements scheduled on Day 5 and Day 7.

For all other procedures (including pre-dose PK sample), the following will not be regarded as protocol deviations:

Table 3. Permitted allowed time windows for all other procedures

Time point (Day 0)	Deviation window in relation to the scheduled time point
Pre-dose	Within 75 min before dosing ¹ (Part 1b: all procedures to be completed before breakfast)
Up to and including 4 h after dosing	± 10 min
After 4 h to 24 h after dosing	± 15 min
More than 24 h after dosing	± 1 hour
Ambulatory visits	Any time on the scheduled day

1. Urine collection for laboratory safety tests will be within 2 h of the scheduled time point and Day 0 urine sample to be collected pre-dose.

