14.5 Clinical Laboratory Evaluations

Data from haematology, coagulation, clinical chemistry and urinalysis will be summarised by treatment.

Urinalysis parameters will also be listed

All laboratory values of potential clinical importance will be listed and all related laboratory results (i.e. haematology or clinical chemistry) for subjects with values of potential clinical importance will be listed, separately. Frequencies of laboratory values of potential clinical importance will be summarised.

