14.6.2 ECG

QT interval data will be presented using Bazett's (QTcB) and Fridericia's (QTcF) corrections.

ECG data will be summarised by treatment and time point. Differences from baseline (Day 0 pre-dose) will be summarised by treatment and time point.

The number of subjects with a potentially clinically important ECG value will be summarised by actual treatment and time point, giving the numbers of subjects with QT, QTcB or QTcF > 450 msec, > 480 msec and > 500 msec, and the numbers of subjects with increases in QT, QTcB or QTcF from baseline of > 30 msec and > 60 msec³. A supporting listing of all subjects with an ECG value of potential clinical importance and a separate listing of ECG findings classified as abnormal by the Investigator will also be provided.

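### The laboratory and ECG tables of potentially clinically important values leave out any subject flagged only at an unscheduled time; one supplementary any-post-dose row would count them

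*SAP*

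**What the plan says.** SAP 12.1 sets a general rule: "Data collected at unscheduled time points during the study will not be used in the summaries or data analyses". The next sentence keeps the data visible: "They will be included in the listings". No exception follows for safety counts.

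Two sets of counts of values of potential clinical importance (PCI) fall under this rule.

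- **Laboratory.** SAP 14.5: "Frequencies of laboratory values of potential clinical importance will be summarised". Under SAP 12.4 a value qualifies when it is both outside the reference interval and further from baseline than the Appendix A limit.
- **ECG.** SAP 14.6.2: "The number of subjects with a potentially clinically important ECG value will be summarised by actual treatment and time point", using QT, QTcB and QTcF cut-offs of 450, 480 and 500 msec and rises of more than 30 and 60 msec. The same section plans "A supporting listing of all subjects with an ECG value of potential clinical importance".

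Shells T_LB1 and T_EG3 are laid out by planned relative time. Neither has a row for any post-dose time.

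Protocol 8.8 provides that, with Sponsor approval, "additional time points may be introduced, and changes to time points may be made". The first ground is better data quality, with the example "if it is believed that an important effect of emodepside is occurring at a time when no measurements are scheduled". The second follows: "or if extra procedures are needed in the interest of subject safety".

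SAP 12.2 treats laboratory repeats separately. A repeat taken before dosing replaces an out-of-range baseline. After dosing, the out-of-range result stays in the summaries and its repeat does not.

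**The concern.** Keeping unscheduled readings out of by-time-point means is sensible. They belong to no planned time, and SAP 12.3 defines no windows that would assign them to one. A PCI table has a different job: it tells the reader how many subjects had a notable value. Extra measurements made because of symptoms or a suspected effect are plausibly more likely to be abnormal than routine ones, although the documents give no data on this.

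Take an ECG done at 5 h, which lies between the 4 h and 6 h nominal times of the schedule, and suppose it shows a QTcF rise above 60 msec. It would be listed, but it would enter no cell of T_EG3.

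The secondary objective is to compare safety and tolerability between formulations. If one arm prompts more extra tests than another, the omission need not fall evenly.

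**Working it through.** **1. Is there a figure to reproduce?** No. The plan states no expected PCI count and no expected number of unscheduled measurements. The only input is 12 subjects per arm (SAP 8.1).

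**2. Which displays does the rule reach?**

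| Display | Effect of SAP 12.1 |
|---|---|
| PCI listings and complete data listings (SAP 12.1, 14.5, 14.6.2, 17.1) | None; unscheduled values are shown |
| T_LB1 and T_EG3, cells at planned times | None; a reading at another time does not belong in them |
| T_LB1 and T_EG3, subjects flagged only at an unscheduled time | Not counted anywhere |
| Vital signs PCI (SAP 14.6.1) | None; listed only, with no count planned |
| Pre-dose laboratory repeats (SAP 12.2) | Used as baseline, so not excluded |
| Repeat of a reading already flagged at a scheduled time | No subject lost; the triggering value is already eligible |

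SAP 11.2 says that categorical summaries take in all recorded values. That could be read as conflicting with 12.1, but it may only mean that every category observed is displayed. It does not settle the matter.

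**3. Direction.** For one arm, let

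- *a* = subjects flagged at a scheduled time but normal on repeat,
- *b* = subjects flagged at a scheduled time and again on repeat,
- *u* = subjects flagged only at an unscheduled time.

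Subjects appearing in at least one cell under the SAP: *a + b*.

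Subjects flagged at any post-dose time: *a + b + u*. Difference, SAP minus any-time: *−u*, so zero or negative.

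Subjects with a confirmed flag or a flag at an added time: *b + u*. Difference, SAP minus this: *a − u*, which can take either sign.

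| a | b | u | SAP | Any-time | Confirmed or added | SAP − any-time | SAP − confirmed or added |
|---|---|---|---|---|---|---|---|
| 0 | 0 | 1 | 0 | 1 | 1 | −1 | −1 |
| 1 | 0 | 0 | 1 | 1 | 0 | 0 | +1 |
| 1 | 0 | 1 | 1 | 2 | 1 | −1 | 0 |

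The positive case arises from the SAP 12.2 rule on laboratory results.

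**4. Size.** Each subject in *u* is 1/12 = 8.3% of an arm. How many there would be cannot be derived. Purely as an assumption, let *q* be the chance that a given subject is flagged only at an unscheduled time, independently across subjects. Then P(at least one missed in an arm) = 1 − (1 − *q*)^12, and the expected number missed is 12*q*.

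| Assumed q | P(at least one missed) | Expected number missed |
|---|---|---|
| 1% | 11.4% | 0.12 |
| 5% | 46.0% | 0.6 |
| 10% | 71.8% | 1.2 |
| 20% | 93.1% | 2.4 |

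This range shows sensitivity only. Nothing in the documents points to one row over another.

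**The case against.** The other side has a good deal to say.

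- **Nothing is hidden.** A reader might infer from SAP 12.1 that unscheduled values are discarded. They are not: they remain in the listings, by subject and treatment, and 12 subjects per arm can be read by eye. This stands. A listing still gives no arm count, and the objective is comparative.
- **Protocol 8.8 is permissive.** A reader might infer that time points are added precisely when an effect is suspected, and that these are then barred. The text requires Sponsor approval, gives a suspected effect as one example, and names subject safety as a separate ground. Neither document says whether an approved added time point is unscheduled for the purposes of SAP 12.1; if it is treated as scheduled, the exclusion does not apply to it. This stands, and is itself a reason to define the term.
- **The counts are not always too low.** The direction is fixed only against an any-time count. Against confirmed laboratory values the count may be too high.
- **No planned percentage moves by 8.3 points.** The shells count results at each planned time, and T_LB1 has no percentage column. The 8.3% applies to an arm-level count that the SAP does not currently produce.
- **Adverse events are another route.** Clinically significant ECG abnormalities become AEs (Protocol 8.11.1), as do laboratory ones meeting the conditions in Protocol 8.11.4, and the AE tables are not laid out by time point. This mitigates the gap but does not close it, because PCI flags are numerical and need no judgement of clinical significance.
- **An any-time count has its own bias.** Arms tested more often have more chances to be flagged, and the study is open-label. This stands and belongs in a footnote.

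**Conclusion.** The point holds as a modest reporting gap. SAP 12.1 makes no exception for the laboratory and ECG PCI tables, and those tables run by planned time only. A subject whose sole post-dose flag is at an unscheduled time is listed and not counted. Relative to an any-post-dose count, the number tabulated is equal or lower, by exactly the number of such subjects. The documents do not support a claim of downward bias against every benchmark, nor any estimate of how often it would happen.

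The conclusion assumes that 12.1 is applied as written and that the measurement in question is treated as unscheduled, which for time points added under Protocol 8.8 is undefined. Safety analysis here is descriptive, with no formal testing, and the primary PK comparisons are untouched. This is a worthwhile improvement rather than a fault that threatens the trial's conclusions.

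**What to change.** Three changes to the SAP:

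1. Limit the exclusion in 12.1 to by-time-point summaries and analyses.
2. State whether a time point added under Protocol 8.8 counts as scheduled.
3. Add one supplementary row per arm to T_LB1 and T_EG3, *any post-dose value, scheduled or unscheduled*, counted by subject.

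The cost is a few sentences and one row per arm in each of two tables. No existing cell changes. The drawback is that arms with more extra tests have more chances to be flagged. A footnote to each table should say so and give the number of unscheduled tests per arm.
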